#### **Treatment of Nivolumab or Ipilimumab Related Infusion Reactions**

Since nivolumab and ipilimumab contain only human immunoglobulin protein sequences, it is unlikely to be immunogenic and induce infusion or hypersensitivity reactions. However, if such a reaction were to occur, it might manifest with fever, chills, rigors, headache, rash, pruritus, arthralgias, hypo- or hypertension, bronchospasm, or other symptoms.

All Grade 3 or 4 infusion reactions should be reported as an SAE if criteria are met. Infusion reactions should be graded according to NCI CTCAE (version 5.0) guidelines.

Treatment recommendations are provided below and may be modified based on local treatment standards and guidelines as appropriate:

**For Grade 1 symptoms:** (Mild reaction; infusion interruption not indicated; intervention not indicated)

Remain at bedside and monitor subject until recovery from symptoms. The following prophylactic premedications are recommended for future infusions: diphenhydramine 50 mg (or equivalent) and/or paracetamol 325 to 1000 mg (acetaminophen) at least 30 minutes before additional nivolumab administrations.

**For Grade 2 symptoms:** (Moderate reaction requires therapy or infusion interruption but responds promptly to symptomatic treatment [eg, antihistamines, non-steroidal anti-inflammatory drugs, narcotics, corticosteroids, bronchodilators, IV fluids]; prophylactic medications indicated

for 24 hours).

Stop the nivolumab or ipilimumab infusion, begin an IV infusion of normal saline, and treat the subject with diphenhydramine 50 mg IV (or equivalent) and/or paracetamol 325 to 1000 mg (acetaminophen); remain at bedside and monitor subject until resolution of symptoms. Corticosteroid or bronchodilator therapy may also be administered as appropriate. If the infusion is interrupted, then restart the infusion at 50% of the original infusion rate when symptoms resolve; if no further complications ensue after 30 minutes, the rate may be increased to 100% of the original infusion rate. Monitor subject closely. If symptoms recur then no further nivolumab or ipilimumab will be administered at that visit. Administer diphenhydramine 50 mg IV, and remain at bedside and monitor the subject until resolution of symptoms. The amount of study drug infused must be recorded on the electronic case report form (eCRF). The following prophylactic pre medications are recommended for future infusions: diphenhydramine 50 mg (or equivalent) and/or paracetamol 325 to 1000 mg (acetaminophen) should be administered at least 30 minutes before additional nivolumab or ipilimumab administrations. If necessary, corticosteroids (recommended dose: up to 25 mg of IV hydrocortisone or equivalent) may be used.

**For Grade 3 or Grade 4 symptoms:** (Severe reaction, Grade 3: prolonged [i.e., not rapidly responsive to symptomatic medication and/or brief interruption of infusion]; recurrence of symptoms following initial improvement; hospitalization indicated for other clinical sequelae [e.g., renal impairment, pulmonary infiltrates]). Grade 4: (life threatening; pressor or ventilator support indicated).

Immediately discontinue infusion of nivolumab or ipilimumab. Begin an IV infusion of normal saline, and treat the subject as follows. Recommend bronchodilators, epinephrine 0.2 to 1 mg of a 1:1,000 solution for subcutaneous administration or 0.1 to 0.25 mg of a 1:10,000 solution injected slowly for IV administration, and/or diphenhydramine 50 mg IV with methylprednisolone 100 mg IV (or equivalent), as needed. Subject should be monitored until the investigator is comfortable that the symptoms will not recur. Nivolumab or ipilimumab will be permanently discontinued. Investigators should follow their institutional guidelines for the treatment of anaphylaxis. Remain at bedside and monitor subject until recovery from symptoms. In the case of late-occurring hypersensitivity symptoms (e.g., appearance of a localized or generalized pruritus within 1 week after treatment), symptomatic treatment may be given (e.g., oral antihistamine, or corticosteroids).

*The section below is Optional and should be considered if part of assessment criteria. All decisions to continue treatment beyond initial progression documented in the study record and part of an agreement with BMS. Subjects should be re-consented with an ICF describing any reasonably foreseeable risks or discomforts.*

### **Treatment Beyond Progression**

Accumulating evidence indicates a minority of subjects treated with immunotherapy may derive clinical benefit despite initial evidence of PD.

Subjects will be permitted to continue treatment beyond initial RECIST 1.1 defined PD as long as they meet the following criteria:

- Investigator-assessed clinical benefit and subject is tolerating study drug.

The assessment of clinical benefit should take into account whether the subject is clinically deteriorating and unlikely to receive further benefit from continued treatment.

Subjects should discontinue study therapy upon further evidence of further progression, defined

as an additional 10% or greater increase in tumor burden volume from time of initial progression (including all target lesions and new measurable lesions).

New lesions are considered measurable at the time of initial progression if the longest diameter is at least 10 mm (except for pathological lymph nodes, which must have a short axis of at least 15 mm). Any new lesion considered non-measurable at the time of initial progression may become measurable and therefore included in the tumor burden measurement if the longest diameter increases to at least 10 mm (except for pathological lymph nodes, which must have an increase in short axis to at least 15 mm).

*For statistical analyses, this will need to be described in patient population information. E.g. Subjects who continue treatment beyond initial investigator-assessed, RECIST 1.1-defined progression will be considered to have investigator-assessed progressive disease at the time of the initial progression event.*

Subjects will have the opportunity to receive all 4 doses of Induction Phase ipilimumab.

#### **Other Immune-mediated Adverse Events**

For suspected immune-related adverse reactions, adequate evaluation should be performed to confirm etiology or exclude other causes. Based on the severity of the adverse reaction, nivolumab or nivolumab in combination with ipilimumab should be withheld and corticosteroids administered. Upon improvement, nivolumab or nivolumab in combination with ipilimumab may be resumed after corticosteroid taper. Nivolumab or nivolumab in combination with ipilimumab must be permanently discontinued for any severe immune-related adverse reaction that recurs and for any life-threatening immune-related adverse reaction.

Patients should be informed of and carefully monitored for evidence of clinically significant systemic irAE (e.g., systemic lupus erythematosus-like diseases) or organ-specific irAE (e.g., rash, colitis, uveitis, hepatitis or thyroid disease). If an irAE is noted, appropriate work-up (including biopsy if possible) should be performed, and steroid therapy may be considered if clinically necessary (see Appendix 3 through 9 for suggested work-up and treatment of irAEs).

It is unknown if systemic corticosteroid therapy has an attenuating effect on ipilimumab activity. However, clinical anti-tumor responses have been maintained in patients treated with corticosteroids and discontinued from ipilimumab. If utilized, corticosteroid therapy should be individualized for each patient. Prior experience suggests that colitis manifested as  $\geq$  Grade 3 diarrhea requires corticosteroid treatment.

## **7.0 OTHER GUIDANCE**

### **7.1 Infusion Reactions Associated with Ipilimumab and Nivolumab**

Infusion reactions should be graded according to Common Terminology Criteria for Adverse Events (CTCAE) Version 5.0 Allergic reaction/hypersensitivity criteria. Severe infusion reactions require the immediate interruption of study drug therapy and permanent discontinuation from further treatment. Appropriate medical therapy including epinephrine, corticosteroids, intravenous antihistamines, bronchodilators, and oxygen should be available for use in the treatment of such reactions. Subjects should be carefully observed until the complete resolution of all signs and symptoms. In each case of an infusion reaction, the investigator should institute treatment measures according to the best available medical practice. The following treatment

guidelines are suggested:

CTCAE Grade 1 Allergic reaction/hypersensitivity (transient flushing or rash, drug fever < 38°C).

Treatment: Decrease the study drug infusion rate by 50% and monitor closely for any worsening.

CTCAE Grade 1 or Grade 2 Allergic reaction/hypersensitivity manifesting only as delayed drug fever (starting after the completion of the study drug infusion).

Treatment: Maintain blinded study drug dose and infusion rate for future infusions.

Consideration could be given to administration of acetaminophen or a non-steroidal anti-inflammatory drug (NSAID) prior to the subsequent study drug infusion, if not otherwise contraindicated in subjects. Dose and schedule of these agents is entirely at the investigator's discretion.

CTCAE Grade 2 Allergic reaction/hypersensitivity (Rash, flushing urticaria, dyspnea, drug fever  $\geq 38^{\circ}\text{C}$ ).

Treatment: Interrupt blinded study drug infusion. Administer bronchodilators, oxygen, etc. as medically indicated. Resume infusion at 50% of previous rate once infusion reaction has resolved or decreased to Grade 1 in severity, and monitor closely for any worsening.

CTCAE Grade 3 or Grade 4 Allergic Reaction/Hypersensitivity: A CTCAE Grade 3 hypersensitivity reaction (symptomatic bronchospasm, requiring parenteral medication(s), with or without urticaria; allergy-related edema/angioedema; hypotension) or a Grade 4 hypersensitivity reaction (anaphylaxis).

Treatment: Stop the study drug infusion immediately and disconnect infusion tubing from the subject. Administer epinephrine, bronchodilators, antihistamines, glucocorticoids, intravenous fluids, vasopressor agents, oxygen, etc., as medically indicated. Contact the Medical Monitor and document as a serious adverse event (Section 6.1). No further study drug treatment to be administered.

#### Treatment of Ipilimumab Related Isolated Drug Fever

In the event of isolated drug fever, the Investigator must use clinical judgment to determine if the fever is related to the ipilimumab or to an infectious etiology.

If a patient experiences isolated drug fever, for the next dose, pre-treatment with acetaminophen or non-steroidal anti-inflammatory agent (Investigator discretion) should be instituted and a repeated antipyretic dose at 6 and 12 hours after ipilimumab infusion should be administered. The infusion rate will remain unchanged for future doses.

If a patient experiences recurrent isolated drug fever following premedication and post dosing with an appropriate antipyretic, the infusion rate for subsequent dosing should be decreased to 50% of the previous rate. If fever recurs following infusion rate change, the Investigator should assess the patient's level of discomfort with the event and use clinical judgment to determine if the patient should receive further ipilimumab.

## 8.0 RADIATION THERAPY GUIDELINES

### 8.1 Planning

After informed consent is obtained, a measurable lesion that is accessible for biopsy is selected by the treating physician as the site for local radiotherapy under Standard of Care practices to establish a diagnosis. The area of interest is imaged at CT planning for conformal treatment. There is no contrast media used in the CT planning. There is an exposure to small amounts of radiation with the use of CT scan. CT scan thickness should be  $\leq 0.5$  cm through the tumor bed region. These images will be used in 3D treatment planning in accordance with the dose specification constraints.

The CTV is defined as the lesion of interest with the expected motion changes, while the PTV is the CTV plus a margin  $\leq 1$  cm, dependent on the anatomical location, to account for setup uncertainty. While gating is not part of the current conformal setting at Stich Radiation Center, WCM, efforts are made to consistently treat chest and abdominal lesions with the patient maintaining shallow breathing, to limit the movement of the volume treated during respiration.

## 8.2 Treatment

Radiotherapy is delivered by external beam using linear accelerators capable of delivering  $\geq 4$  MV x-rays. The PTV will encompass all or part of the biopsied NSCLC lesion, and will be defined by the treating physician. The PTV will be treated daily, Monday-Friday. A dose of 30 Gy in 5 fractions of 6 Gy each is delivered, daily, to an isodose surface encompassing  $\geq 90\%$  of the PTV.

Radiation Dose specification: The planning target volume receives a minimum of 90% of the prescription dose.

Treatment Machine: A linear accelerator with  $\geq 4$  MV x-rays is required.

Immobilization Technique: Patients will be set-up for treatment and CT scanning, and planned for treatment. The specific immobilization technique will be determined at the discretion of the treating physician.

Target Positioning Verification: Digitally acquired radiographic images will be used to verify the position of the target with respect to the treatment machine's isocenter using digitally reconstructed radiographs (DRRs) as a reference image set. Both kV and MV images may be used to verify setup.

IGRT Target Localization: In addition to the portal imaging, cone-beam CT (CBCT) images will be acquired prior to treatment for each fraction. By using IGRT to image the tumor bed in "real-time", the operator may automatically align the tumor bed with the treatment machine on each day of treatment. If shifts are made based upon the CBCT images, the portal images will be repeated.

Treatment Planning: 3D-Conformal or IMRT treatment planning is allowed. This includes "field-in- field" beams as well as the use of dynamic multi-leaf collimator (MLC) derived using inverse planning or electronic compensator techniques. Field arrangements and technique should be chosen that satisfy the PTV dose coverage constraints and normal tissue dose constraints using Dose-Volume Histogram (DVH) analysis. By carefully selecting the gantry and table angle combinations that do not enter or exit through other organs of the body, the dose can be confined to the traditional treatment volumes. Non-coplanar beam arrangements are encouraged, but not required. Dose calculations with tissue inhomogeneity correction must be used. In view of the GI pattern of toxicity of ipilimumab, particular attention will be applied to limit exposure to the bowel. To mitigate this risk, normal tissue constraints of abdominal and pelvic organs will be employed from recommendations from AAPM Task Group 101 (66) and the H. Lee Moffitt Cancer Center experience using this fractionation schedule (67).

After completion of the first course of radiation + ipilimumab at a 3mg/kg dose on Day 1 (or within 24 hours of RT), the patient will start on day 22 the regimen of Nivolumab 360 mg q3 weeks and Ipilimumab 1mg/kg q6 weeks until evidence of progression.

Response assessment will be performed during Day 70 ( $\pm$  7 days) by imaging with PET/CT or CT (CAP).

### **8.3 Treatment Modifications for Radiation Adverse Events:**

**Dosing delay:** Except for radiation-associated mucositis and skin toxicity, the patient should have resolution or return to pre-treatment baseline of all grade 3-4 toxicities prior to the start of the next immunotherapy treatment.

### **8.4 On Study Evaluations**

As summarized in the Study Calendar, patients are evaluated pre-treatment for definition of metastatic sites with PET/CT or CT (CAP). At least two measurable metastatic sites are identified, and one of these lesions will be selected by the investigator for RT treatment with the goal of minimizing potential toxicity from RT. All lesions are followed per modified WHO criteria.

### **8.5 Off Study Criteria**

- Intercurrent illness that prevents further administration of treatment,
- Unacceptable toxicity (defined in Section 15),
- Patient decides to withdraw from the study, or
- General or specific changes in the patient's condition render the patient unacceptable for further treatment in the judgment of the investigator.
- Authorized Physicians must notify the data manager and Principle Investigator when a patient is taken off study.

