Assessment of response: Response is defined as an objective radiographic response of the measurable metastatic site(s) outside the radiation field evaluated by CT at 3 months after the start of treatment. Lesions will be measured using RECIST 1.1 [52] and best response (PR + CR) based on these criteria will be recorded. To reduce confounding, the irradiated lesion will be excluded from baseline measurement and measurement for the assessment of in-field response will be recorded separately.

**Objective 2.2:** To enhance the ORR to the combination of Ipi/Nivo in NSCLC by preceding it with a combination of Ipi/RT to convert the irradiated tumor into an in situ vaccine.

The trial is designed to enhance ORR to the combination of Ipi/Nivo, by an initial induction of Ipi/RT to one of the metastatic lesions. Since a) approximately 2/3 of chemo-refractory metastatic NSCLC cancers are expected to express  $<1\%$  PDL1; b) Checkmate 012 demonstrated a 19%

objective response rate (ORR) in these patients and c) our recent study of radiation and ipi demonstrated 18% ORR based on intent to treat, the current trial is powered to test in patients with metastatic NSCLC whether the initial addition of local radiotherapy during ipilimumab can increase the ORR to immune checkpoints independently from PD-L1 expression. In order to test this hypothesis a Simon's two-stage design is chosen for this trial, thus 15 patients will be enrolled in the first stage with an upper limit of 4 responses for 1st stage rejection of the combined regimen. If 5 or more objective responses are seen then the trial will proceed to the second stage and an additional 29 patients with PD-L1 negative tumors will be enrolled and treated, for a total target accrual of 44 evaluable patients. A patient is deemed evaluable if they have measurable disease at baseline and had a 9 week imaging evaluation. To ensure 44 evaluable patients, up to 4 additional patients will be enrolled if necessary to replace patients who withdrew or did not have a 9 week evaluation. If there are more than 44 evaluable patients, the decision rule will be made based on the first 44 evaluable patients. Patients who were replaced because they were not evaluable, will not be part of the denominator.

[figure not shown]
**Objective 2.3:** To explore whether early changes in TCR repertoire in peripheral blood are associated with response to treatment

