### **Discontinuation Criteria**

Treatment should be permanently discontinued for the following:

Any Grade 2 drug-related uveitis or eye pain or blurred vision that does not respond to topical therapy and does not improve to Grade 1 severity within the re-treatment period OR requires systemic treatment

Any Grade 3 non-skin, drug-related adverse event lasting > 7 days, with the following exceptions for drug-related laboratory abnormalities, uveitis, pneumonitis, bronchospasm, diarrhea, colitis, neurologic adverse event, hypersensitivity reactions, and infusion reactions

Grade 3 drug-related uveitis, pneumonitis, bronchospasm, diarrhea, colitis, neurologic adverse event, hypersensitivity reaction, or infusion reaction of any duration requires discontinuation

Grade 3 drug-related laboratory abnormalities do not require treatment discontinuation except those noted below

Grade 3 drug-related thrombocytopenia > 7 days or associated with bleeding requires discontinuation

Any drug-related liver function test (LFT) abnormality that meets the following criteria require discontinuation:

- AST or ALT > 8 x ULN
- Total bilirubin > 5 x ULN
- Concurrent AST or ALT > 3 x ULN and total bilirubin > 2 x ULN

Any Grade 4 drug-related adverse event or laboratory abnormality, except for the following events which do not require discontinuation:

Isolated Grade 4 amylase or lipase abnormalities that are not associated with symptoms or clinical manifestations of pancreatitis and decrease to < Grade 4 within 1 week of onset.

- Isolated Grade 4 electrolyte imbalances/abnormalities that are not associated with clinical sequelae and are corrected with supplementation/appropriate management within 72 hours of their onset
- Any dosing interruption lasting > 6 weeks with the following exceptions:
- Dosing interruptions to allow for prolonged steroid tapers to manage drug-related adverse events are allowed. Prior to re-initiating treatment in a subject with a dosing interruption lasting > 6 weeks, the Investigator must be consulted. Tumor assessments should continue as per protocol even if dosing is interrupted
- Dosing interruptions > 6 weeks that occur for non-drug-related reasons may be allowed if approved by the Investigator. Prior to re-initiating treatment in a subject with a dosing interruption lasting > 6 weeks, the Investigator must be consulted. Tumor assessments should continue as per protocol even if dosing is interrupted

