## 11.0 PROCEDURES BY VISIT

### Study Completion or Early Discontinuation Visit

At the time of study early withdrawal, the reason for early withdrawal and any new or continuing AEs should be documented. There are two levels of withdrawal and it should be documented whether one or both levels are met. The first level is withdrawal from protocol treatment and testing schedule. The second level is withdrawal from all subsequent follow-up (e.g. disease progression and overall survival). A patient may choose to withdraw from further treatment and protocol assessments but is willing to be followed for disease progression and survival.

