## 12.0 STUDY DRUG DISCONTINUATION

- Intercurrent illness that prevents further administration of treatment,
- Unacceptable toxicity (defined in Section 4.3.3.1),
- Patient decides to withdraw from the treatment, or
- General or specific changes in the patient's condition render the patient unacceptable for further treatment in the judgment of the investigator.

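### Sections 8.5 and 12.0 give the same three events different consequences (off study or off drug only), so a patient who stops drug without progression can miss the week-9 scan and drop out of the ORR denominator

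*Combined protocol and SAP*

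**What the plan says.** Section 8.5 (Off Study Criteria) has three events that reappear in Section 12.0 (Study Drug Discontinuation):

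- "Intercurrent illness that prevents further administration of treatment", in the same words in both sections.
- "General or specific changes in the patient's condition render the patient unacceptable for further treatment in the judgment of the investigator", also the same in both.
- Unacceptable toxicity, with different pointers: "Unacceptable toxicity (defined in Section 15") in 8.5 and "Unacceptable toxicity (defined in Section 4.3.3.1") in 12.0.

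The remaining patient-level item differs, and properly so. In 8.5 the patient withdraws from the study; in 12.0 the patient withdraws from treatment.

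Section 11.0 describes two levels of withdrawal. "The first level is withdrawal from protocol treatment and testing schedule"; the second ends all later follow-up. It adds that a patient may leave treatment and assessments yet agree to be followed for progression and survival.

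In Section 6.0, the Discontinuation Criteria say "Tumor assessments should continue as per protocol even if dosing is interrupted". The sentence stands under the exceptions for dosing interruptions longer than 6 weeks.

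Section 4.0, Objective 2.2, makes the scan decisive: "A patient is deemed evaluable if they have measurable disease at baseline and had a 9 week imaging evaluation". Patients without it may be replaced, up to 4 of them, and those replaced are left out of the denominator.

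**The concern.** Two of the three shared items in 8.5 are framed around further treatment no longer being possible. They are reasons to stop drug, placed under a heading that ends study participation. A site that follows 8.5 takes such a patient off study. A site that follows 12.0 stops drug and nothing more. The trial has two sites, and the Administrative Section has sub-sites manage the study under local guidelines, so practice can differ.

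The patients at issue stop for toxicity, illness or clinical change before the day-70 assessment and without progression. Whether they are scanned decides whether they count in the stage 1 rule (5 of 15) and the final rule (18 of 44). The section a site follows could thus change who is in the primary analysis, for reasons that may be related to outcome. Patients taken off study may also be censored early for PFS, TTP and DOR.

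**Working it through.** **1. Does any passage settle the conflict?**

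| Place | What it supports | Why it does not settle the point |
|---|---|---|
| Section 6.0, opening | CT for all patients at day 70 | Does not mention patients already off study |
| Section 13.4, Efficacy Evaluation | Imaging at day 70, then every 3 months until progression | Does not say that this survives an off-study decision |
| Section 16.1 | Post-treatment follow-up, as appropriate, after events that cause discontinuation | Concerns adverse-event follow-up; names no scan |
| Section 11.0 | Progression and survival follow-up possible after leaving treatment | Depends on the patient's willingness; level 1 joins treatment to the testing schedule |
| Section 6.0, Discontinuation Criteria | Tumor assessments continue | Covers interruption, not permanent discontinuation |
| Section 15 | Nothing at patient level | Trial suspension rule based on counts of grade 4+ events |
| Section 4.3.3.1 | Nothing | In neither the contents nor the text |

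The likely intent is continued assessment. No passage overrides 8.5.

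**2. Reproduce the design.** Inputs from Section 17: null rate 0.31, alternative 0.51, 15 then 29 patients, continue with 5 or more responses. The final threshold of 18 is from the Synopsis and the primary analysis section.

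P(success | p) = Σ over x = 5 to 15 of b(x; 15, p) × P(Bin(29, p) ≥ 18 − x)

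- p = 0.31: 0.0946, within the stated 0.10.
- p = 0.51: 0.9000, the stated 90%.

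Section 17.2 prints 17 as the threshold. That gives 0.1498 and 0.925, so the stated error rates belong to 18, which is used below.

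**3. Illustrate the loss.** The documents do not say how many patients would miss the scan. Assume m of 48 do, for m up to the 4 replacement places, with the share q = m/48 applying equally in both stages.

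*If all those lost are non-responders* and the all-treated rate is 0.31, the rate among evaluable patients is 0.31/(1 − q). For m = 4: 0.31/(44/48) = 0.3382.

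*If all those lost are responders* and the all-treated rate is 0.51, the rate among evaluable patients is (0.51 − q)/(1 − q). For m = 4: (0.51 − 0.0833)/0.9167 = 0.4655.

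| m | Non-responders lost: evaluable rate | False-success chance | Responders lost: evaluable rate | Power |
|---|---|---|---|---|
| 0 | 0.310 | 0.095 | 0.510 | 0.900 |
| 1 | 0.317 | 0.112 | 0.500 | 0.877 |
| 2 | 0.323 | 0.131 | 0.489 | 0.848 |
| 3 | 0.331 | 0.154 | 0.477 | 0.814 |
| 4 | 0.338 | 0.181 | 0.466 | 0.773 |

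In the first case with m = 4, a minimum success of 18/44 (40.9%) is 18/48 (37.5%) of those treated.

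**The case against.** The best defence is that the protocol, read as a whole, keeps these patients under observation. Section 6.0 re-images all patients at day 70 with no on-drug condition. Section 13.4 ends imaging at progression, not at the last dose. Section 16.1 provides follow-up after discontinuation for adverse events, and the Synopsis sets follow-up at 5 years or until death. Section 8.5 also sits inside the radiation therapy guidelines and may not have been meant to govern toxicity in the ipilimumab/nivolumab phase. This stands as evidence of intent. It does not remove an off-study list whose items are general and which no other passage limits to radiation.

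Three stronger readings are tempting and are not supported.

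- *A reader might infer that stopping drug ends the scans, and that these patients are censored early for OS as well.* The documents make this possible, not established. Section 11.0 puts loss of progression and survival follow-up at a separate second level. Equally, Section 12.0 does not itself promise a scan.
- *A reader might apply the 11-13% treatment-related discontinuation in Figure 7 to 48 patients.* That gives 5.3 to 6.2 patients and a 62-76% chance of exceeding the 4 replacement places. It requires every stop to fall before the week-9 scan and every such patient to miss it. Figure 8 gives a median follow-up of 11.8 to 12.9 months for those arms, which had no radiation/ipilimumab induction. If half the stops fell that early (an assumption), the chance is 12-20%; if a quarter did, 1-2%.
- *A reader might take Table 2 as showing that the lost patients are mostly responders* (5/17 with severe or serious immune events responded, against 2/39 without). It is a 56-patient ipilimumab series in melanoma with 7 responders, and the text beside it says there are no NSCLC data. A severe immune event is also not the same as stopping drug. The table shows that loss could be related to response; it does not fix the direction.

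**Conclusion.** The point holds in limited form. Three events carry conflicting consequences in Sections 8.5 and 12.0; patient withdrawal is not in conflict. Both toxicity cross-references fail. No sentence secures the week-9 scan after permanent discontinuation without progression. These findings rest on the text and are firm.

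The size is not known. With 1 to 4 of 48 patients lost, the chance of a false success rises to 0.11-0.18 if all are non-responders and the all-treated rate is 31%. If all are responders and the rate is 51%, power falls to 0.88-0.77. These are the two extremes for that many losses; a mixture lies between them. The effect on PFS, TTP and DOR is possible early censoring and cannot be sized from the documents. The protocol should be corrected, because the rule decides who enters the primary analysis and the remedy is cheap.

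**What to change.** - Reconcile Sections 8.5, 11.0 and 12.0 so that each event has one stated consequence for study participation, and repair both cross-references for unacceptable toxicity. Which clinical rule stops treatment is for the sponsor.
- State, as a data-collection rule, that after permanent drug discontinuation without progression the day-70 scan, the scheduled scans until progression and survival follow-up continue unless the patient withdraws consent for them.
- In Section 11.0, separate patients who stop treatment but continue assessments from those who stop both.
- Extend the tumor-assessment sentence in the Discontinuation Criteria to permanent discontinuation.

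The cost is a wording amendment, since the scans and visits are already in the study calendar. The downside is that some patients who have stopped drug attend scheduled scans they might otherwise have skipped.
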